Background & Rationale	
Alzheimer’ disease and dementia are common, and feared. Recent scientific advances have underscored the significant population attributable risk of modifiable risk factors including those whose modification particularly when combined could delay or prevent dementia. However, there is an important gap in having this opportunity translated by individuals to make lifestyle changes and address their personal risk factors to preserve their brain health and preventing dementia. The preventive message does not fit the medical model well and the opportunity is not reaching the public or engaging it through public health programs that can intervene to bridge the gap. Healthy Actions and Lifestyles to Avoid Dementia or Hispanos y el ALTo a la Demencia program (HALT- AD) is a novel bilingual educational program that will focus on reducing risk factors with the ultimate goal of preventing dementia. It will be centered around a web-based interactive virtual online platform that will be developed to be dynamic, engaging, and interactive. HALT-AD will be complemented by remote facilitated support discussion groups which will focus on the content of the educational material and the invocation of change through participant engagement and compliance.
 
Prior to launching the full HALT-AD program, it is essential that we conduct a preliminary pilot study to evaluate the program’s first prototype including: the usability of- and engagement with- the online platform, users’ acceptability of the learning content and facilitated support discussion groups. As well, effectiveness of the program in changing knowledge, self-efficacy, and dementia-related lifestyle risk measures will be assessed.
 
This initial four-months pilot study will focus on at least three educational courses (such as: introduction to dementia and risk factors, sleep, diet, and social connectivity). The information generated from this study will help inform the development of the second program’s prototype, expected to benefit from the initial pilot to become more user-friendly, effective and accessible to our target audience.

Study Design	This pilot study will be a longitudinal study of an inception cohort exposed to the HALT AD online educational program for a four month study. It will utilize pre- and post- intervention collection of quantitative and qualitative data to evaluate the program’s first prototype.
Target Population	
 • Cognitively normal midlife and older-adult participants will be eligible to participate in this pilot study with the following inclusion criteria; Ages 50-85

	
 • Montreal Cognitive Assessment-Telephone/Blind version (T-MoCA) Score $\geq 18/22$ • Sufficient proficiency in English or Spanish to undergo clinical assessment and participate in an online educational program. • Technical ability to participate in an online educational program (i.e. computer/tablet and internet access; ability to send and receive emails) • Sufficient vision and hearing to participate in online educational program (judgement of site investigator)
Number of Participants	
A total of 20 participants will be enrolled at UCSD
 
 • 10 participants will complete the English version of HALT-AD • 10 participants will complete the Spanish version of HALT-AD 
We are aiming to recruit 50% women and to enroll a diverse participant sample across varied age ranges within both language groups.

Study Duration	
Estimated duration of the entire pilot evaluation period is approximately 4 months (including participant enrollment, pilot study, focus groups and completion of data collection)
 
 • Individual HALT-AD participation: 3 Months participation in online HALT-AD program
Study Goal and Aims	
Overall Goal: To conduct a preliminary pilot study to evaluate the first prototype of HALT-AD.
 
Aims:
 
 1. To evaluate engagement with- the online platform 2. To evaluate preliminary evidence on the effectiveness of the program in changing 
 a) knowledge, b) self-efficacy, and c) dementia-related lifestyle risk factors. 3. To determine users’ acceptability of the program content 4. To determine users’ acceptability and satisfaction with the facilitated support discussion groups 5. To evaluate the usability of the online platform
Outcome Measures	
Primary Outcome Measures:
 
 1. Users’ engagement with- the HALT-AD online platform as measured by: 
 • The total amount of time (in minutes) spent per user on all courses combined

	
 • The percentage of participants who completed all courses 
Secondary Outcome Measures:
 
 1. Preliminary evidence on the effectiveness of the program in changing knowledge, self-efficacy, and dementia-related lifestyle risk factors will be evaluated by: 
 • Change from baseline in knowledge on the HALT-AD knowledge assessment survey at 4 months • Change from baseline in self-efficacy on the New General Self-Efficacy Scale at 4 months • Change from baseline in lifestyle risk on the HALT-AD Lifestyle Risk Assessment Survey at 4 months 
Exploratory Outcome Measures:
 
 1. Users’ acceptability of the HALT-AD program content will be determined by: 
 • HALT-AD Course Acceptability Survey • Focus group discussion 2. Users’ acceptability and satisfaction with the facilitated support discussion groups will be determined by: 
 • Facilitated support discussion group Acceptability Survey • Focus group discussion 3. The usability of the online platform will be evaluated by: 
 • HALT-AD User Experience Survey • Net Promotor Score Survey

Statistical Plan
	
Descriptive statistics will be used for quantitative data. Change scores will be computed where applicable. Change = (4 months score - baseline score). Continuous data will be presented with mean, standard deviations, median, minimum and maximum and 95% confidence intervals. Categorical data will be presented as proportions and percentages. Changes in continuous outcome measures between baseline and post-intervention will be analyzed by repeated measures t-test.
 
Qualitative data generated from focus groups, logs, and open-ended survey questions will be thematically analyzed using inductive qualitative coding.
 
Sample Size and Power
 
Given that this pilot study is being conducted to contribute to the development of the HALT-AD program, we did not power to detect an

	intervention effect size over time. The sample size for the pilot was estimated based on prior experience in the development of similar programs.
--	---

TABLE OF CONTENTS

LIST OF ABBREVIATIONS:	9
1.0 INTRODUCTION	10
1.1 BACKGROUND	10
1.2 RATIONALE	10
2.0 STUDY DESIGN	11
3.0 STUDY GOAL AND AIMS	11
3.1 OVERALL GOAL	11
3.2 AIMS	11
4.0 OUTCOME MEASURES	12

16.2	APPENDIX 3: SCREENING QUESTIONS	37
16.2.1	PRE-SCREENING TELEPHONE INTERVIEW	37
16.2.2	HEARING AND VISION	40
16.3	APPENDIX 4: BASELINE ASSESSMENTS	43
16.3.1	SOCIODEMOGRAPHIC INFORMATION	43
16.3.2	MEDICAL HISTORY	46
16.3.3	CURRENT MEDICATIONS	51

LIST OF ABBREVIATIONS:

AD	Alzheimer's Disease
ADRD	AD and related dementias
AE	Adverse event
BMI	Body Mass Index
CMS	Centers for Medicare and Medicaid Services
CRF	Case Report Form
HALT-AD	Healthy Actions and Lifestyles to Avoid Dementia
ICF	Informed Consent Form
NGSE	New General Self-Efficacy
NPS	Net Promoter Score Survey
T-MoCA	Montreal Cognitive Assessment-Telephone/Blind Version
UEQ	User Experience Questionnaire
ICMJE	International Committee of Medication Journal Editors

1.0 INTRODUCTION

1.1 Background

Alzheimer's disease (AD) is the single most feared disease associated with aging [1, 2], having a devastating social and economic impact on patients, families, and the community [3]. With its aging demographic, the growth of affected Americans is exponential with one person diagnosed every 67 seconds in the United States. The annual cost of AD to the US economy is over \$260 million [4]. Over 84,000 individuals have AD in San Diego county alone [5], and 690,000 across California. There is a 35% increase projected within approximately the next decade [3]. Coinciding with these general trends for America's aging population, there are currently just over 4 million Hispanic Americans ages 65 and over in this group, which is projected to grow to almost 20 million by 2060 [6], with 3.6 million having AD [7]. Currently, close to half (45%) of all older Hispanic Americans are living in two states, California and Texas. Given that this population is disproportionately affected by social determinants leading to poor health outcomes placing them at increased risk of AD [8], the development of culturally informed preventive interventions that target modifiable risk factors to reduce dementia risk in Hispanics is paramount.

Progress in finding effective pharmaceutical treatments to modify or definitively treat AD and related dementias (ADRD) has been extremely disappointing [9]. Recent research underscores a population attributable risk of 28.2% associated with a range of modifiable risk factors across the lifespan [10], and encouraging results from studies combining multiple risk factors as a focus of their intervention [11]. In turn, efforts to successfully modify lifestyle and other health factors (e.g., vascular health, physical activity, diet, sleep etc.) addressing personalized risk could have an enormous long-term benefit in delaying or preventing dementia. While the medical sector and Centers for Medicare and Medicaid Services (CMS) are constantly innovating individual service delivery [12], insufficient attention has been given to systematically translating biomedical research on lifestyle changes to reduce dementia risk through information at the population level that can promote effective behavioral change. Indeed, this approach is our best current opportunity for dementia risk reduction.

1.2 Rationale

Healthy Actions and Lifestyles to Avoid Dementia or Hispanos y el ALTo a la Demencia program (HALT- AD) is a novel bilingual educational program that will focus on reducing risk factors with the ultimate goal of preventing dementia. It will be centered around a web-based interactive virtual online platform that will be developed to be dynamic, engaging, and interactive. Through interactive courses, the educational content of HALT-AD will provide guidance on modifiable lifestyle risk factors and the identification of treatable medical conditions including cerebrovascular health, sleep, sensory loss, social isolation, mood, diet, and physical activity.

Participants in HALT-AD will be provided with personalized risk profiles, will be encouraged to learn about their risk factors and how they can effectively modify them, and will be provided with feedback on their progress. They will participate in facilitated support discussion groups,

which will focus on the content of the educational material and the invocation of change through participant engagement and compliance.

Prior to launching the full HALT-AD program, it is essential that we conduct a preliminary pilot study to evaluate the program's first prototype. At the end of the 3-month pilot program, evaluations will include: the usability of- and engagement with- the online platform and users' acceptability of the learning content and facilitated support discussion groups. As well as, evaluating preliminary evidence on the effectiveness of the program in changing knowledge, self-efficacy, and dementia-related lifestyle risk factors. The program will also be evaluated on metrics such as being user friendly, engaging, supportive and communicative, with the potential for scalability to state- and national-levels.

This initial four-months pilot study will focus on at least three educational courses (introduction to dementia and lifestyle risk factors, sleep and diet). It may also include a fourth educational course on social connectivity and loneliness. Completion of this initial pilot study will allow for a round of improvements informed by data from the program, on usability, as well as feedback from participants and citizen advisors. This will allow for an iterative process to build the program to its full content, with feedback to optimize the user experience and ensure the accessibility of the content. The information generated from this study will help inform the development of the second program's prototype, expected to benefit from the initial pilot to become more user-friendly, effective and accessible to our target audience.

2.0 STUDY DESIGN

This pilot study will be a longitudinal study of an inception cohort exposed to the HALT AD online educational program for a four-month study. It will utilize pre- and post- intervention collection of quantitative and qualitative data to evaluate the program's first prototype.

3.0 STUDY GOAL AND AIMS

3.1 Overall Goal

To conduct a preliminary pilot study to evaluate the first prototype of HALT-AD.

3.2 Aims

1. To evaluate engagement with- the online platform
2. To evaluate preliminary evidence on the effectiveness of the program in changing knowledge, self-efficacy, and dementia-related lifestyle risk factors
3. To determine users' acceptability of the program content
4. To determine users' acceptability and satisfaction with the facilitated support discussion groups

5. To evaluate the usability of the online platform

4.0 OUTCOME MEASURES

4.1 Primary Outcomes

- 4.1.1 Users' engagement with- the HALT-AD online platform as measured by:
 - the total amount of time (in minutes) spent per user on all courses combined
 - the percentage of participants who completed all courses

4.2 Secondary Outcomes

- 4.2.1 Preliminary evidence on the effectiveness of the program in changing knowledge, self-efficacy, and dementia-related lifestyle risk factors will be evaluated by:
 - Change from baseline in knowledge on the HALT-AD knowledge assessment survey at 4 months
 - Change from baseline in self-efficacy on the New General Self-Efficacy Scale (NGSE) at 4 months
 - Change from baseline in lifestyle risk on the HALT-AD Lifestyle Risk Assessment Survey at 4 months

4.3 Exploratory Outcomes

- 4.3.1 Users' acceptability of the HALT-AD program content will be determined by:
 - HALT-AD Course Acceptability Survey
 - Focus group discussion
- 4.3.2 Users' acceptability and satisfaction with the facilitated support discussion groups will be determined by:
 - Facilitated Discussion Group Acceptability Survey
 - Focus group discussion
- 4.3.3 The usability of the online platform will be evaluated by:
 - HALT-AD User Experience Survey
 - Net Promotor Score Survey

5.0 ETHICS AND REGULATORY CONSIDERATIONS

5.1 Electronic Informed Consent

For the purposes of this study, the consent process will be completed remotely. A telephone call with the participant and a study coordinator will be scheduled in order to facilitate the informed consent discussion and to address any questions from the participant.

The electronic Informed Consent Form (ICF) will be maintained in REDCap. Participants will review the consent information and electronically sign the ICF directly within REDCap. The REDCap e-Consent Framework provides standardized tools to obtain consent and store consent documentation with a certification screen and a storage function which automatically generates a ‘hard-copy’ PDF of the signed form. Participants will be able to download and keep a copy of the ICF for their records. The completed PDFs will be securely stored in REDCap’s File Repository and will only be accessible to the program manager, study coordinators and Co-Principle Investigators (co-PIs). These files will be kept separate from other study data maintained in REDCap, which will be de-identified and coded by Participant ID only (see Figure 2 (page 23) for a description of how study will be entered and stored in REDCap)

It will be made clear to each potential participant that informed consent may be withdrawn at any time without needing to give a reason and that such withdrawal will not compromise the relationship between the participant and the Investigator nor the participant’s future treatment.

The ICF will be provided in a language fully comprehensible to the prospective participants and ample opportunity must be given to inquire about the details of the study.

5.2 Potential Risks and Benefits Associated with this Study

5.2.1 Potential Risks

Risks associated with study participation are minimal and may include fatigue and/or frustration associated with cognitive screening at baseline and participating in an online educational program. Questionnaires on mood and lifestyle risk may increase negative affect. In order to mitigate these risks, participants will be reminded they can skip questions or take breaks. If a participant mentions negative emotions, the study coordinator will alert [name], co-PI and clinical psychologist, who will attempt to contact the participant within 48 hours to suggest mental health resources.

There may be limits in protecting confidentiality during facilitated group discussions and focus groups. Participants will be reminded to keep group discussions confidential but this cannot be guaranteed.

5.2.2 Potential Benefits

Participants in this study may experience benefits from participating in a web-based educational program including increased knowledge and engagement regarding ways to promote their brain health, and possible positive reduction in their risk profiles, though such improvement cannot be predicted with any certainty. This study is expected to benefit the general community in the future by promoting public interest, literacy, and engagement in lifestyle interventions for brain health and dementia prevention through dissemination of HALT-AD to the broader public.

6.0 PARTICIPANT SELECTION

A total of 20 participants will be enrolled at UCSD with 50% (n=10) completing the English version of HALT-AD and 50% (n=10) completing the Spanish version. We are aiming to recruit

50% women and to enroll a diverse participant sample across varied age ranges within both language groups.

6.1 Inclusion Criteria

Participants must meet all of the following inclusion criteria to be eligible for enrollment:

1. Signed informed consent must be obtained and documented (from the participant).
2. Sufficient proficiency in English or Spanish to undergo clinical assessment and participate in an online educational program.
3. Ages 50-85
4. Montreal Cognitive Assessment-Telephone/Blind Version (T-MoCA) score $\geq 18/22$
5. Technical ability to participate in an online educational program (i.e. ability to operate a computer/tablet and gain internet access; ability to send and receive emails)
6. Sufficient vision and hearing to participate in online educational program (judgement of site investigator)
7. Ability to sit comfortably for a period of at least 30 minutes

6.2 Exclusion Criteria

1. Participants who, in the opinion of the co-PIs, are not able to complete trial procedures or adhere to the schedule of study assessments will be excluded from study participation.
2. Individuals where English or Spanish is not sufficiently proficient for clinical assessment, and participation in a web-based educational program.
3. Participants who do not have sufficient vision and hearing to participate in an online educational program
4. Individuals who do not have the technical ability to participate in an online educational program. Technical ability is defined as ability to operate a computer/tablet and gain internet access; ability to send and receive emails)
5. Total Score on the T-MoCA < 18
6. Individuals who have an advanced degree (e.g. Master's, MD, PhD) in an area related to brain health will not be eligible to participate.

7.0 STUDY PROCEDURES

7.1 Study Visits

The schedule of study visits and procedures to be performed at each visit are outlined below and summarized in the Schedule of Events table (Appendix 1). A detailed description of study procedures is located in Section 8.0. and a detailed description of study instruments is located in Section 9.0

7.1.1 Remote Study Visits

Pre-screening and screening visits will be conducted remotely over telephone. Participants will need access to a computer or mobile device in order to participate in HALT-AD and complete baseline and follow-up surveys on REDCap.

7.1.2 Pre-Screening Telephone Questionnaire (within a month prior to baseline)

Interested participants will be invited to complete a brief pre-screening questionnaire over telephone with a study team member to ascertain potential eligibility for the study. Participants will be asked to provide verbal assent prior to completing the questionnaire. Questions will include age, education, language fluency and access to technology needed to participate in the study. Total time to complete the pre-screening questionnaire is approximately 5-10 minutes.

7.1.3 Telephone Screening (within a month prior to baseline)

Following the pre-screening procedures described above, potentially eligible participants will be invited to complete the electronic informed consent process (see section 5.1). Once participants have electronically signed the ICF, the following procedures will be conducted remotely via telephone during the screening period (Estimated Time to Complete: up to 1 hour). Screening procedures may be completed over multiple days as long as all procedures are completed within 30 days prior to baseline. Procedures and instruments will be adapted for remote administration (see section 8.0 Study Procedure Descriptions and section 9.0 Study-Specific Instruments).

The following procedures will be conducted during the screening period (Estimated Time: 1.0-1.5 hours):

- Review of inclusion/exclusion criteria
- T-MoCA
- Hearing and Vision assessment
- Evaluation and confirmation of eligibility

Following completion of the screening assessments above, the co-PIs will be responsible for confirming participant eligibility to be enrolled in the study.

7.1.4 Baseline/ HALT-AD Program Launch (+/- 30 days)

Participants who are confirmed to be eligible to participate and enrolled in the study, will then complete the following baseline assessments. These may be completed on the same day as the screening visit, as long as they are conducted following the screening assessments and confirmation of eligibility (total estimated time approximately 30 min):

- Documentation of demographics, medical history (including past medical procedures and family history), medications
- Self-Report Height, Weight
- Body Mass Index (BMI) calculation (based on self-report current height and weight)
- Knowledge Assessment Survey

Following completion of the above baseline assessments, participants will be enrolled in the HALT-AD online program and will be provided with instructions for logging into and beginning their participation in the program (see section 7.2 for a complete description of HALT-AD).

Participants will also complete the following baseline assessments directly within the online HALT-AD program (total estimated time approximately 30 min-1.0 hour):

- New General Self-Efficacy Scale (NGSE)
- Lifestyle Risk Assessment
- Goal setting

Throughout the participants' participation in the 3-Month HALT-AD program, a study coordinator will maintain contact with the participant by telephone or email to check-in with participants, provide reminders about upcoming HALT-AD program elements and be available to answer any questions that may arise. E-mails will be sent from a secure UCSD health e-mail account.

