9.2.2 The New General Self-Efficacy Scale

Self-Efficacy is a concept that refers to one's global confidence in their ability to cope with demanding or novel situations. The New General Self-Efficacy scale is an 8-item 5-point likert scale (strongly disagree (1) to strongly agree (5)) which measure one's perceived competence in dealing with a range of stressful or challenging situations [14]. The scale will be completed online within HALT-AD.

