16.0 APPENDICES

APPENDIX 1: Schedule of Events

UCSD HALT-AD PILOT STUDY SCHEDULE OF EVENTS						
PROCEDURES	SCRE NING	BASELINE	MONTH 1	MONTH 2	MONTH 3	MONTH 4
Remote Study Procedures (on Zoom or REDCap)						
ELECTRONIC INFORMED CONSENT (E-CONSENT)	X					
INCLUSION/EXCLUSION CRITERIA EVALUATED	X					
SOCIODEMOGRAPHICS		X				
MEDICAL/SURGICAL/FAMILY HISTORY		X				
WEIGHT, HEIGHT (participant estimates) and BMI		X				
HEARING AND VISION ASSESSMENT	X					
MONTREAL COGNITIVE ASSESSMENT (MoCA)	X					
HALT-AD USER EXPERIENCE SURVEY						X
NET PROMOTER SCORE SURVEY						X
HALT-AD COURSE ACCEPTABILITY SURVEY						X
KNOWLEDGE ASSESSMENT SURVEY		X				X
FACILITATED DISCUSSION GROUP ACCEPTABILITY SURVEY						X
FOCUS GROUPS						X
HALT-AD Online Assessments						
NEW GENERAL SELF-EFFICACY SCALE (NGSE)		X				X
LIFESTYLE RISK ASSESSMENT (Diet, Sleep, Mindfulness)		X				X
GOAL SETTING AND REVIEW		X				X
FACILITATED DISCUSSION GROUPS ¹			X*	X*	X*	

¹ *Facilitated Discussion Groups will occur approximately every three weeks in between Months 1-3. They will occur prior to the start of each new content module.

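### Does the unanchored window of plus or minus 30 days on Baseline/Launch leave the timing of the baseline measurements undefined?

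*Combined protocol and SAP*

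**What the plan says.** Three timing rules meet at the baseline visit.

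- The heading of section 7.1.4 reads "Baseline/ HALT-AD Program Launch (+/- 30 days" and gives no reference date. The Schedule of Events (Appendix 1) shows a baseline column with no window.
- Section 7.1.3 lets screening run over several days provided "all procedures are completed within 30 days prior to baseline". Section 7.1.2 uses the same direction of counting: "Pre-Screening Telephone Questionnaire (within a month prior to baseline".
- The body of section 7.1.4 allows baseline on the screening day "as long as they are conducted following the screening assessments and confirmation of eligibility".

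Section 7.1.4 then splits the baseline measurements. History, height and weight, and the Knowledge Assessment Survey come first: "Following completion of the above baseline assessments, participants will be enrolled in the HALT-AD online program". The New General Self-Efficacy Scale (NGSE), the Lifestyle Risk Assessment and goal setting follow on the platform: "Participants will also complete the following baseline assessments directly within the online HALT-AD program". Section 9.2.2 says of the NGSE only that "The scale will be completed online within HALT-AD".

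**The concern.** A window without a reference date cannot be audited by itself, and this one is twice as wide as the gap the neighbouring text allows between screening and baseline. A coordinator might take a visit to be within the window in 7.1.4 when it is outside the limit in 7.1.3. The baseline date matters in three places: it decides whether screening is still current (7.1.3), it starts adverse event collection (11.0, 11.1), and it supplies the score subtracted in the change calculation (12.1).

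The NGSE adds a second worry. The Knowledge survey must be finished before platform access, but the NGSE is completed after login instructions are given. If the plus side of the window let someone complete it after starting a course, the baseline score would already reflect some of the intervention, and the change in self-efficacy, a secondary outcome, would not be a true before-and-after difference.

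**Working it through.** The plan gives no figure to reproduce here, because section 12.2 states that the study is not powered for change. The check is a day count followed by a comparison of passages.

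**1. Screening date held fixed.** Let day 0 be a one-day screening.

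- Order rule (7.1.4): baseline on day 0 or later.
- Limit (7.1.3): baseline on day 30 or earlier.
- Permitted range: 0 to 30, which is 30 days wide.
- Heading window around reference day r: r − 30 to r + 30, which is 60 days wide.

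For r between 0 and 30, the part outside the permitted range is (30 − r) days before screening plus r days past the limit, so (30 − r) + r = 30 days.

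| r | Days before screening | Days past limit | Total outside |
|---|---|---|---|
| 0 | 30 | 0 | 30 |
| 15 | 15 | 15 | 30 |
| 30 | 0 | 30 | 30 |

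That is 30/60 = 50% by width, or 30/61 = 49% counted in calendar days. If screening is spread over 10 days and the window is counted from the last of them, the permitted days are 0 to 20 (21 days), and 61 − 21 = 40 of 61 fall outside. The arithmetic is right, but it depends on fixing screening first.

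**2. Screening counted back from baseline, as 7.1.3 and 7.1.2 write it.** Let L be a planned launch date, B the actual baseline and S the screening date.

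- Heading: L − 30 ≤ B ≤ L + 30.
- Sections 7.1.3 and 7.1.4: B − 30 ≤ S ≤ B.

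For any B in the window, an S that meets the second line exists. At the late end, B = L + 30 allows S from L to L + 30. At the early end, B = L − 30 allows S from L − 60 to L − 30. No day in the window has to break a rule.

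**3. Window counted from the participant's own platform access.** The plus side does not fit the history items and the Knowledge survey, which must precede access. The stated order then governs, and those items cannot be late.

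**4. Whether a real visit can become ambiguous.** Take r = 15 and baseline on day 45. It is 45 − 15 = 30 days from the reference date, so it is within the heading window. It is also 45 − 30 = 15 days past the limit in 7.1.3. The two rules apply together, so this is a deviation from 7.1.3 whatever the heading says.

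**5. What depends on the reference date.** Section 11.0 starts adverse event collection at the baseline visit, and section 12.1 subtracts the baseline score. Both use what actually happened. The primary outcomes in 4.1, minutes on courses and the percentage completing all courses, use no baseline score.

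**6. NGSE order.** These passages bear on it:

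- Section 7.1.4 lists it as a baseline assessment, alongside the Lifestyle Risk Assessment and goal setting.
- Section 7.2.3.1 places the Lifestyle Risk Assessment at the start of participation, and 7.2.3.2 bases the goals on the resulting risk profile.
- Appendix 1 puts the NGSE under baseline and Month 4 only. Its footnote says of the discussion groups, held in Months 1 to 3, that "They will occur prior to the start of each new content module".
- Section 2.0 describes collection before and after the intervention.

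All of these point to an NGSE taken before course content, and none points the other way. Figure 1, cited in 7.2.2 for the steps at enrolment, is not reproduced in the available text, so its absence cannot be counted against the plan.

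**The case for a change.** The best case for a change is that the window works only with a reference date the protocol never states. If it is counted from screening, the whole minus side is impossible, because baseline would come before the assessments that establish eligibility. The overall timetable adds some weight: about 4 months in total with 3 months of individual participation leaves roughly 4 − 3 = 1 month for enrolment and everything else, which sits awkwardly with a 60-day window. The NGSE is a listed secondary outcome, yet it lacks the explicit sentence that the Knowledge survey has. Repairing both would take two sentences.

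What stands is the missing reference date, and the poor fit of the minus side if screening is the reference. What does not stand is that the documents must contradict each other: the planned-launch reading is unstated, but the joint heading permits it and it removes the conflict. Even without that reading, a wide tolerance does not override a narrower rule beside it. On the NGSE, a sentence would record an order that the baseline label, the schedule and the pre/post design already imply. No error is shown that platform enforcement or extra date fields would prevent, and 13.1.1 already provides for raw programme data to be exported by participant.

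**Conclusion.** No change to the plan is called for. The omission is real but clerical: section 7.1.4 does not name the date its 30 days are counted from. The apparent conflict is 30 of 60 days if screening is fixed and the reference date lies 0 to 30 days after it. It is zero if the window surrounds a planned launch date and screening is scheduled back from the actual baseline. In either case the order rule in 7.1.4 and the 30-day limit in 7.1.3 decide whether a visit complies.

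The primary outcomes and the Knowledge change are unaffected. The effect on the NGSE change is zero if baseline is applied literally; the documents give nothing from which to estimate an effect otherwise. The conclusion assumes that staff apply the narrower rules alongside the heading and administer the in-platform baseline set at the start of participation, as the rest of the protocol indicates. Naming the reference date when the document is next edited would be tidy, but it would not alter any analysis or conclusion.
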